- SA1: Compare the extent of change pre-test to post-test in walking and mobility outcomes, social and vocational participation, and quality of life between the identical evidence-based individualized exercise program delivered via GEMS-S or GEMS-T in adults with MS who have slowed walking (greater than 6 seconds on the T25FWT);
- SA2: Evaluate and compare the effectiveness between participants randomized to their preferred delivery mode (GEMS-T(Choice) or GEMS-S(Choice)) and those who are not randomized to their preferred delivery mode (GEMS-T or GEMS-S);
- SA3: Evaluate changes in self-efficacy, and adoption of exercise between these groups (GEMS-T, GEMS-S, GEMS-T(Choice), GEMS-S(Choice)).

RESEARCH METHODS

Design

This is a multi-site, 2-staged randomized, choice design study aimed at noninferiority, to compare the effectiveness of delivering an individualized exercise program in a facility (facility-based exercise training or GEMS-S) versus via telerehabilitation (telerehab-based exercise training or GEMS-T) in people with MS. Noninferiority assumes both interventions (GEMS-S and GEMS-T) produce no statistically different outcomes.

Shepherd Center is the Clinical Coordinating site, led by [name], and UAB is the Training Site, led by [name]. UAB will also house the Statistical Center, led by [name]. The Data Management Center led by [name] will be maintained by iConquerMS of the Accelerated Cure Project.

This protocol will first outline site specific procedures and tools, and then will provide details regarding the coordination of the multiple study sites by the investigators at the Shepherd Center.

Participants

We will enroll 400 participants across the following eight centers: The Shepherd Center, Atlanta, GA; the University of Georgia, Athens; the Cleveland Clinic Mellen Center for MS Treatment and Research, Ohio; the University of North Carolina, Chapel Hill; Massachusetts General Hospital, Boston (MGH); the University of Colorado; the University of Alabama, Birmingham (UAB) in collaboration with The Tanner Center and Foundation for Neurological Diseases (Tanner Center); and Marquette University, Wisconsin. The criteria for eligibility will be identical at all sites. Participants will qualify for the study if they meet the following criteria:

Inclusion criteria:

1. Physician-confirmed diagnosis of MS
2. Expanded Disability Status Scale (EDSS) score of 4.0 through 6.5
3. Age between 18 and 65 years

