4. Able to travel to a GEMS-S site for testing and training
5. Accessible, technological platform for GEMS-T (i.e. computer or DVD player and TV,

and telephone)

6. A score of between 25 and 75 on the MSWS-12
7. Timed 25-foot walk test (T25FWT) time of between 6 seconds and 3 minutes
8. Medically stable or approval from physician to participate in exercise studies
9. A score of between 3 and 6 (inclusive) on the Patient Determined Disability Steps

Exclusion criteria:

1. Documented MS relapse in the past 30 days
2. Have had falls in the past three months that the study investigator determines makes participation unsafe
3. Unable to walk 25 feet
4. Already exercises at recommended levels as determined by a score of 25 or higher on the Godin Leisure-Time Exercise questionnaire
5. Has other neurological (e.g., stroke) or musculoskeletal conditions or other co-morbidities
6. Has cognitive difficulties as determined by a Mini Mental Status Exam score <19
7. Is not proficient in English
8. Is physically unable to complete the second T25FWT trial
9. Any other concern that the investigators deem would jeopardize the safety of the potential participant.

We will randomize 200 participants to the Choice group and 200 to the No Choice group. Those in the Choice group will choose which exercise program to undertake – GEMS-T or GEMS-S. In the No Choice group, we will randomize 100 participants to GEMS-S and 100 to GEMS-T (see Figure 1). Four sites (Shepherd Center with help from UGA, Marquette University, Cleveland Clinic, and University of Colorado) will each recruit 80 participants. UNC and MGH will together recruit a total of 40 participants. UAB will recruit at least 40 participants with help from the Tanner Center, a Birmingham-based multidisciplinary center providing neurology, nursing, infusion, clinical research, neurodiagnostic testing, occupational therapy, physical therapy, speech/language pathology, licensed professional counseling, group wellness classes, and individual personal training in one central location.

[figure not shown]

Figure 1: Randomization Scheme for Each Participant

Recruitment methods

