If a physician instructs a participant to pause exercising, the site research coordinator must obtain medical clearance from the participant's physician before resuming exercise. If the participant's physician does not instruct a participant to stop exercising, the site PI determines whether or not medical clearance after an AE is required.

Site research coordinators will inform the participant's coaches when medical consent has been obtained and the participant is approved to resume exercising.

Figure 3 below provides additional detail regarding how AEs are reported and addressed.

[figure not shown]
[figure not shown]

Figure 3: AE Reporting and Follow up Procedures

DATA ANALYSIS

Data analysis plan

The primary hypothesis is a non-inferiority test of the changes in T25FWT between GEMS-T and GEMS-S. This will be tested using a linear model with site as the stratification factor and an intention to treat approach. The primary analysis will adjust for covariates age, gender and baseline EDSS or PDDS. Further addition of covariates may be examined in sensitivity analyses based on any differences seen on examination of baseline variables between groups. Secondary endpoints include change in 6MWT and EDSS/PDDS. In all endpoints, we are assessing

improvement over baseline values. We will examine the frequency of worsening as a safety comparison. We will also examine the primary endpoint of a 20% improvement in the T25FWT (yes or no) using logistic regression. Further, to characterize the changes over time, we will use linear mixed models to assess the slopes of change for GEMS-S versus GEMS-T groups. We will also examine the relationship between the dose of exercise measured by compliance and the change in the primary and secondary outcomes. These are exploratory outcomes to see if the compliance measures predict the benefits on the outcomes. This information is important for translation and information dissemination to people with MS.

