Data-source adequacy. All data will be collected specifically for this prospective research; thus, all needed covariates will be collected by the trained research staff. There will be a standard measurement manual and quality control procedures will be implemented. Each evaluator will be trained in data collection for the various outcome measures; new research personnel will also be trained as they join the study team. Data collection training will also be repeated annually. Demographic and disease related data will be collected and will allow us to examine confounding variables, such as age (i.e. people with MS who are older may walk more slowly than those who are younger); type of assistive device (i.e. people with MS who use a walker may walk more slowly than those who do not use an assistive device); type of MS (i.e. people with MS who have RRMS may perform better than those with progressive forms of MS). Data for the study will be derived from several validated instruments and through participant assessment at enrollment and follow up PROs via iConquerMS. The use of these different data sources and modes of data collection provides some modest redundancy, while minimizing the amount of missing data, to assure that all outcomes are appropriately ascertained. Data will be entered in the HIPAA- compliant database maintained by iConquerMS with oversight by [name]. Sites will be responsible for maintaining all aspects of the database entered from the clinic and staff support from iConquerMS will be available to trouble shoot technical questions. Access to this data will be restricted to study personnel only. Individual site coordinators will each have a unique username and password to enter the participant information. Research data will be entered online through the secure system and source documents will be kept in a secure fashion. Staff from iConquerMS will monitor and track errors, completeness with routine reports and feedback to the sites. Data will be shared with the Statistical Center at UAB, who will provide analyses using SAS, SPSS, R and other programs, as necessary.

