Data linkage plan. Each participant will be assigned a study ID number when randomized to the intervention group by the biostatistician. This will be the only identifier in all databases and systems used in this study. The Shepherd Center will maintain the master file. None of the investigators or staff involved in the assessments will have access to the identifier data, and thus will remain blinded to the assignment for the entire intervention phase.

Sensitivity analyses. Randomization should balance covariates across treatment groups, but this will be checked with frequency and means tables, and chi-square/Fisher exact and F-tests/t-tests respectively. If treatment groups show important imbalances among covariates, then they can be adjusted for using covariates in various types of regression models as we noted above under the primary analyses. As noted briefly in the primary analysis section, per protocol analyses will be used to support the conclusions of the intention to treat analyses. In the intention to treat analyses we must take into account dropouts. For anyone with at least one post randomization timed walk test, we will impute a model based final endpoint to assess change. Key sensitivity analyses will include adjustment for covariates: age, gender, sex and treatment preference at entry. Interaction terms will be used to identify potential impacts of key covariates. In addition, imputation for missing values will be conducted to assess the impact of these lost observations. We note again that rules are in place to deal with the time variables. For other variables (MSWS, MFIS and NeuroQOL, EDSS) will require various forms of imputation for sensitivity analyses. We will use a general approach discussed below for imputation of these secondary endpoints and use per protocol versus ITT for sensitivity analysis. For the major analyses, best case and worst case analyses will be done. Subgroup analyses will attempt to quantify the consistency of the findings amongst subgroups.

Management of missing data

a. Methods to prevent and monitor missing data.

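### Covariates beyond the fixed set are chosen by baseline significance tests and an undefined judgement of imbalance, although 200 of 400 participants choose their delivery mode

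*SAP*

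**What the plan says.** **Design.** Protocol, Participants, on the first stage: "We will randomize 200 participants to the Choice group and 200 to the No Choice group". At the second stage, mode is settled in one of two ways: "Those in the Choice group will choose which exercise program to undertake", while "In the No Choice group, we will randomize 100 participants to GEMS-S and 100 to GEMS-T". Mode of delivery is therefore randomised for 200 participants and self-selected for 200.

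**Fixed covariates.** SAP, SA1, fits a linear model with site as stratification factor, adjusted for age, gender and baseline EDSS (the Protocol's Data analysis plan has EDSS or PDDS). SA2 uses the same models with a Choice-by-treatment interaction and contrasts of the four cells. SA3 and the patient-reported outcomes follow the same pattern.

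**Further covariates.** Both documents leave these to sensitivity analyses, "based on any differences seen on examination of baseline variables between groups". SAP, Sensitivity analyses, starts from the premise that "Randomization should balance covariates across treatment groups" and says "this will be checked with frequency and means tables, and chi-square/Fisher exact and F-tests/t-tests respectively". Imbalances thought important may then be adjusted for. There is no candidate list, no threshold and no p-value rule. The same paragraph names age, gender, sex and preference for a treatment on entry as covariates for the key sensitivity analyses, without any test.

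**Known confounders.** SAP, Data-source adequacy, lists age, MS type and "type of assistive device (i.e. people with MS who use a walker may walk more slowly" as confounding variables.

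**The concern.** Among the 200 participants randomised to a mode, any baseline difference is chance, so a significance test answers no useful question. Among the 200 who choose, balance cannot be presumed. A non-significant test there does not show that a prognostic variable is harmless, because the test may simply lack power.

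The SAP applies one procedure, built on the randomisation premise, to both situations. Two variables that plausibly predict both the chosen mode and the change in walking time have no assured place: assistive device and baseline T25FWT. They would enter only if someone judged the observed imbalance important, after seeing the data.

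At stake is the credibility of every mode comparison that includes choosers. Some confounding may remain, and the adjustment set would be open to the charge of having been picked after the fact.

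**Working it through.** The documents give no figure on this point to reproduce. The check has three parts.

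**1. Which comparisons include choosers**

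- Sample: "We will enroll 400 participants across the following eight centers". Choosers are 200/400 = 50%. The No Choice arms are 100 + 100 = 200.
- The SA2 and SA3 four-cell contrasts include choosers by definition.
- For the primary contrast the documents are open. The SAP's labels in SA2 and SA3 keep the Choice cells separate from TET and FET, which suggests 100 v 100. The Protocol's Intervention section gives n=200 for each mode, which is possible only if choosers are counted.

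**2. Where each confounder has a fixed place**

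| Variable | Primary/SA2/SA3 model | Key sensitivity set | Elsewhere |
|---|---|---|---|
| Age | yes | yes | HTE |
| MS type | no | no | HTE: interaction added to the SA2 model, and risk model for worsening |
| Assistive device | no | no | none |
| Baseline T25FWT | no | no | none as a covariate |

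Adjusting for treatment preference does not fill the gap. Within the Choice half, preference and mode received are the same variable. In the No Choice half, Protocol Table 1 shows no preference item; the Choice form in the notes after that table is for the Choice group only.

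**3. How the tests behave**

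Assumptions not in the documents: two-sided 5% tests, independent covariates, and even uptake in the Choice half.

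*Randomised half.* The chance of at least one false flag among k tests is 1 − 0.95^k: 23% for k = 5, 40% for k = 10, 64% for k = 20.

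*Pooled 200 v 200.* An imbalance of D SD among choosers is diluted to D/2. Approximate power is Φ((D/2)·√(200/2) − 1.96).

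| D among choosers | Pooled imbalance | Chance of a flag |
|---|---|---|
| 0.2 | 0.10 | 17% |
| 0.3 | 0.15 | Φ(1.5 − 1.96) = 32% |
| 0.4 | 0.20 | 52% |
| 0.6 | 0.30 | 85% |

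If the test were run within the Choice half alone (100 v 100), the figures would be 29% at 0.2 SD, 56% at 0.3 SD and 81% at 0.4 SD.

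*Effect on the estimate.* A simulation of 4,000 runs per setting used no true mode effect, 100/100 randomised plus 100/100 self-selected, and one prognostic covariate with correlation 0.3 or 0.5 to the outcome. Each cell gives bias in SD, then two-sided type I error; ranges run over the two correlations.

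| D | No adjustment | Adjust if p < 0.05 | Always adjust |
|---|---|---|---|
| 0.3 | 0.045–0.075; 8.1–11.6% | 0.020–0.033; 5.7–5.9% | about 0; 5.1–5.6% |
| 0.6 | 0.088–0.150; 14.5–32.1% | 0.004–0.011; 5.4–5.6% | about 0; 5.1–5.6% |

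The unadjusted bias at D = 0.3 agrees with correlation × D/2: 0.3 × 0.15 = 0.045 and 0.5 × 0.15 = 0.075.

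Monte Carlo error on a 5% rate is √(0.05 × 0.95/4000) = 0.34 percentage points, so the type I error gap between the last two columns is close to noise. The bias gap at D = 0.3 is not: the estimate's standard error is about √(1/200 + 1/200) = 0.10 SD, and 0.10/√4000 = 0.0016.

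In the randomised 100 v 100 alone, at correlation 0.5, test-then-adjust gave bias 0.002 SD and type I error 4.4%, so it did no harm.

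**The case against.** Four points can be made for the plan, and much of them stands.

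- **Most of the adjustment is fixed.** A reader might infer that baseline tests decide the covariates of the adjusted analyses in general. They do not. The primary model and the key sensitivity set are named in advance, and the data-driven step concerns further, optional covariates only.
- **MS type is not left to a test.** A reader might infer that every confounder the SAP names needs a significant test to enter. That fails for MS type, which the HTE section adds to the SA2 model by a pre-specified interaction, and for age. It is true of neither variable, and even for assistive device no significance cut-off is stated: the tests stand beside descriptive tables and the trigger is a judgement of importance. The 5% rule in the calculation is an assumption. The documented gap is that the judgement is undefined.
- **The premise of balance is sound for part of the trial.** Randomisation covers Choice v No Choice and the two No Choice arms. If the primary contrast is 100 v 100, the procedure does no harm there. It does not cover contrasts involving the Choice cells, which SA2 and SA3 plan under any reading.
- **The shown harm is small.** Type I error barely moves under test-then-adjust, and bias is at most 0.033 SD at the imbalances tried. This limits the weight of the point. It is not a reason to keep the step, since fixed adjustment costs nothing and removes that bias.

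**Conclusion.** The point holds as a modest improvement to the SAP. For comparisons that include choosers, the step that selects extra covariates rests on a premise that does not apply to half the sample, uses tests with limited power, and ends in an undefined judgement. Assistive device and baseline T25FWT have no fixed place in any model, and MS type has one only through the heterogeneity analyses.

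With a 0.3 SD imbalance among choosers, the pooled test flags it about one time in three, and 0.020 to 0.033 SD of bias remains. At 0.6 SD the test usually flags it and the remaining bias is 0.004 to 0.011 SD. These sizes rest on the assumed 5% tests, even uptake, one covariate and a correlation of 0.3 to 0.5. Several confounders could add up or cancel.

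The documents do not support the conclusion that the primary analysis is compromised: its covariates are fixed, and it may not include choosers at all.

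**What to change.** In the SAP, Sensitivity analyses:

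1. Drop the chi-square, Fisher, F- and t-tests as a step for selecting covariates. Report baseline standardised differences descriptively, separately for the randomised and the Choice halves.
2. Pre-specify baseline T25FWT, assistive device and MS type, together with site, age, gender and baseline EDSS, for every mode comparison that includes Choice participants and for the covariate sensitivity analysis.
3. Remove the open-ended provision for imbalances judged important, or label anything added under it as post hoc.

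This wording works whether the primary contrast is 100 v 100 or pooled, but the SAP should also say which it is. Fixed adjustment deals only with measured covariates, so comparisons among choosers remain observational as to mode and should be reported as such.

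The cost is SAP wording. T25FWT is measured at Visit 1 and MS type is in the enrolment survey (Protocol, Table 1). Device type is anticipated in SAP, Data-source adequacy, and device use is passed to the coach (Protocol, Transfer of participant to coach). The one thing to confirm is that device is held as a baseline field in the study database.

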collection. We will use multiple imputation using SAS Proc MI and Proc MI analyze with 5 replicates per imputed dataset. We also will develop a propensity score within treatment group derived via a logistic regression analysis for prediction of the major missingness. The reason for using propensity scores is that if the proportion of missingness is low, covariate adjustment for multiple imputation can be dominated by the characteristics of those with the data and not those without. Item non-response for the scales will be dealt with per the instructions of the validated scales. The half rule will be used if there isn't a standard for the validated questionnaire unless the assumption of non-hierarchy of the question does not hold. If less than 3% of data are missing, the issue will be ignored and "complete-case analysis" will be used.⁸⁷ If, as expected, more than 3% of the data are missing (due to refusals or drop-outs, for example), then we will use multiple imputation for all analyses. The current expectation is that the "chained equations" (or, "fully conditional specification") method will be used in imputing the missing values. We expect to use a minimum of 100 sets of imputed values.

- c. **Validated methods to deal with missing data that properly account for statistical uncertainty due to missingness.** We will use multiple imputation with Rubin's rules for estimating uncertainty, including imputation uncertainty. As noted above, we will use PROC MI and MI Analyze with five replicates per assessment so that variability will consist of both estimation uncertainty (within estimate variability) and variability between the imputed data sets. Diagnostic checks of the imputations will be used (see 6.e., below)

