- d. **Recording and reporting reasons for dropout and missing data and account for all patients in reports.** There will be several logs that will be maintained by the site RC, including site Training log, Adverse Events log, and Enrolled Participants log. Participants in both the facility-based (FET) or telerehab (TET) group will record their training each session in a log-book. The Pedometer data will also be monitored to determine adherence to the exercise program. Participants will record missed sessions and the reason for the miss, and if the sessions was made up during the corresponding week. For FET, the site RC will collect the log-books on a weekly basis; for TET, participants will mail the log-book to the site on a monthly basis. The site RC will enter the data into the central database. In addition, for TET, the coach will obtain information about missed sessions during the video-chat sessions and document these in the database. Any missed training or assessment sessions will be reported to the site RC. If any participant is dropped from the study, the data and reason will be documented in the site Enrollment Log. This information will be summarized annually for the site-specific IRBs as well as for the Shepherd (Primary site) IRB, the Advisory Board, and the DSMB, and will be reported in the Final Project report.
- e. **Examining sensitivity of inferences to missing data methods and assumptions and incorporate them into interpretation.** Multiple imputation assumes that the data are Missing at Random (MAR). Sensitivity analysis here means checking that the results do not change qualitatively (the conclusion is the same) under other assumptions. We will use the following methods for our sensitivity analyses: (1) a weighting approach (the different imputed values are given different weights) as suggested in Carpenter, J.R., Kenward, M.G., and White, I.R. (2007),⁸⁵ The weights are chosen empirically and will mimic a Not Missing at Random assumption; (2) varying the imputed values by multiplying them by a fixed value; this allows one to emulate, say, a pattern-mixture model. Discussions of this appear in van Buuren, S. (2012)⁸⁶ and Raghunathan, T. (2016).⁸⁷ Note that van Buuren, among others⁸⁸ also discusses diagnostic checks on the imputations and these will be used also. If imputations fail the diagnostic checks, we will change our imputation model and re-impute (and re-run the diagnostic checks).

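### The SAP states both 5 and at least 100 imputations and gives no departure for its Not-Missing-at-Random weighting check; with 5, the check is too weak to test a moderate departure

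*SAP*

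**What the plan says.** All of this is in the SAP, under Management of missing data.

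- **Number of imputations.** Item b says "We will use multiple imputation using SAS Proc MI and Proc MI analyze with 5 replicates per imputed dataset", and item c repeats that "we will use PROC MI and MI Analyze with five replicates per assessment". Item b also says, in connection with chained equations, "We expect to use a minimum of 100 sets of imputed values". Nothing reconciles the two figures or assigns either to the sensitivity analyses.
- **Standard for robustness.** Item e acknowledges that the imputation rests on MAR and adds: "Sensitivity analysis here means checking that the results do not change qualitatively (the conclusion is the same) under other assumptions".
- **Method (1).** Imputed values receive unequal weights, following a published method. "The weights are chosen empirically and will mimic a Not Missing at Random assumption". No departure size, range, delivery mode, weight formula or weight diagnostic is given.
- **Method (2).** This consists of "varying the imputed values by multiplying them by a fixed value", to emulate a pattern-mixture model. Neither the factor nor the delivery mode is stated.

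The SAP's Sensitivity analyses paragraph adds best-case and worst-case analyses for the major analyses, without defining them. The analysis being protected is the non-inferiority comparison of T25FWT change between telerehabilitation (GEMS-T, called TET in the SAP) and facility delivery (GEMS-S, called FET).

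**The concern.** A weighted mean lies between the smallest and largest of the values averaged. If method (1) weights whole imputed datasets, it can move the estimated mode difference only as far as the least favourable MAR imputation. With few imputations that distance is short. The conclusion may then stay the same because the check could not move, not because the data withstood the departure.

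The word empirically does not fill the gap. Observed data do not identify how far missing outcomes depart from MAR, so the departure has to be stated in advance.

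For a non-inferiority claim the harmful case is missing GEMS-T walkers doing worse than MAR implies. Missing T25FWT values are likely here: the protocol's COVID-19 follow-up section suspends the clinical measures during site restrictions, the protocol allows immediate full withdrawal, and the SAP expects more than 3% missing. What is at stake is agreement under method (1) being reported as evidence of robustness when the check had little chance of disagreeing.

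**Working it through.** Neither document has a figure to reproduce: no margin, alpha, SD, power or dropout rate is stated for the 400 participants.

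**Inputs**
- From the protocol: 200 per delivery mode with Choice and No Choice pooled (Intervention section); 100 per randomised No Choice arm.
- From the SAP: M = 5 or M ≥ 100 imputations.
- Assumed: SD 1; missing fraction f equal in both modes; missing GEMS-T outcomes worse than MAR by δ SD; truth exactly at the margin, so every non-inferiority result is false; one-sided alpha 0.025; margin 0.28 SD, which 200 per mode supports at 80% power.
- Assumed weights: dataset level, proportional to exp(δ × sum of imputed GEMS-T values), with the true δ.

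**Step 1: reach.** With n_m = fn missing and n_o = n − n_m observed per mode, the between-imputation SD of the mode difference is √[2f²(1/n_o + 1/n_m)]. The largest of 5 draws lies on average 1.163 SDs above the centre, and the largest of 100 lies 2.508. The shift needed is f × δ.

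- f = 15%: √[2 × 0.0225 × (1/170 + 1/30)] = 0.042. Reach is 0.049 (M = 5) or 0.105 (M = 100). Needed: 0.0375, 0.075 and 0.150 for δ = 0.25, 0.5 and 1.
- f = 20%: √[2 × 0.04 × (1/160 + 1/40)] = 0.050. Reach is 0.058 or 0.125. Needed: 0.050, 0.100 and 0.200.

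On average, five imputations reach 0.25 SD but not 0.5 SD; 100 reach 0.5 SD but not 1 SD.

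**Step 2: decision.** Simulation with proper normal imputation per mode and Rubin's rules, 200 per mode, f = 20% (6000 trials per row; 1500 for M = 1000). Kept means still non-inferior after the check, among trials where the MAR analysis falsely claimed non-inferiority. Effective number is 1/Σw².

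| δ | Shift needed | M | Mean move | Effective number | Kept, weighting | Kept, true shift |
|---|---|---|---|---|---|---|
| 0.25 | 0.050 | 5 | 0.026 | 2.4 | 0.811 | 0.352 |
| | | 100 | 0.058 | 14.8 | 0.388 | 0.364 |
| | | 1000 | 0.063 | 79.3 | 0.238 | 0.381 |
| 0.5 | 0.100 | 5 | 0.033 | 1.7 | 0.797 | 0.186 |
| | | 100 | 0.080 | 4.1 | 0.369 | 0.178 |
| | | 1000 | 0.102 | 8.0 | 0.209 | 0.164 |
| 1.0 | 0.200 | 5 | 0.036 | 1.3 | 0.854 | 0.064 |
| | | 100 | 0.087 | 1.9 | 0.499 | 0.057 |
| | | 1000 | 0.117 | 2.4 | 0.334 | 0.045 |

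The rates are conditional, so Monte Carlo error is a few points. For δ = 0.5 and M = 1000, about 1500 × 0.134 = 201 false claims give a standard error of √(0.209 × 0.791/201) ≈ 0.03.

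**Step 3: benchmark.** The target is not zero. A correctly shifted analysis still errs in about 2.5% of trials. At δ = 0.5 the MAR analysis falsely claims non-inferiority in about 13.4% of trials, so the ideal check keeps about 2.5/13.4 = 19% of those claims.

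**Step 4: a caution on calibration.** Because proper imputation also draws the mean, these weights aim at fδ(1 + n_m/n_o), not fδ. At f = 20% and δ = 0.25 that is 0.05 × (1 + 40/160) = 0.0625, which matches the 0.063 observed. The low 0.238 in that row is therefore over-correction. At δ = 0.5 the aim is 0.125, so the 0.102 move at M = 1000 falls short of the weights' own target while happening to match the shift needed.

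**Step 5: sensitivity to the assumptions.** With M = 5, the share kept was 0.73–0.92 over all scenarios run (f = 5–30%, 100 or 200 per mode). It was 0.78–0.82 at one-sided alpha 0.05. With margins of 0.20–0.40 SD it was 0.81–0.82, or 0.73–0.80 with truth at 1.25 times the margin. With M = 100 the range over all scenarios was 0.27–0.65.

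**The case against.** **The SAP also says at least 100.** This stands. A reader might infer that the plan commits to five imputations and would therefore call a false result robust about four times in five. The documents do not support that: the minimum of 100 appears in the same section, and with 100 the share kept at 0.5 SD is roughly half as large. The defect is the unresolved number together with the unstated departure.

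**Other checks exist.** This also stands. Method (2) and the best/worst-case analyses are not confined to the range of the MAR draws, so the rates above are not the error rate of the whole sensitivity plan. But method (2) states neither factor nor mode, and a common factor applied to both modes would largely cancel in the difference. As written, neither check makes up for a weak method (1).

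**The weighting scheme is assumed.** The SAP does not say whether weights attach to single values or whole datasets, and the cited source was not available. If each participant's five imputed values were weighted separately, the average reach in one mode would be about 1.163f: 0.17 at 15% and 0.23 at 20%, enough even for 1 SD. The range limit therefore holds only on the dataset-level reading, and the percentages hold only for exponential weights.

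**Missingness may be small.** The SAP does not expect large proportions missing. The 15–20% is an assumption, but the M = 5 result changes little over 5–30%.

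**Conclusion.** The concern holds conditionally. The SAP leaves both the number of imputations and the departure undefined for a check it labels Not Missing at Random. Assume dataset-level exponential weights, 200 per mode, 15–20% missing, truth at the margin and a 0.5 SD departure in GEMS-T. The check then keeps about 75–80% of false non-inferiority claims with 5 imputations, 35–40% with 100 and 20–25% with 1000, against about 18–25% when the true shift is applied (0.16–0.19 in the 20% runs tabulated). At 0.25 SD, 100 imputations perform about as well as the true shift. At 1 SD even 1000 leave about 32–36% against 4–10%.

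Two stronger readings are not supported. Reweighting MAR imputations is not invalid in itself: with enough imputations it moves far enough for small and moderate departures. Nor does the check agree whatever the missing outcomes are: even with five imputations it overturns about a fifth of the false claims. All rates are conditional on a false claim having occurred and describe method (1) alone. This is a weakness in a supporting analysis, not in the primary model.

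**What to change.** 1. In items b and c, reconcile 5 with 100. For method (1), remove the five-replicate statements and specify a separate large set of imputations, for example at least 1000.
2. In item e, replace the empirical choice of weights with weights computed from a pre-stated series of departures for missing T25FWT, set by delivery mode (for example 0.25, 0.5 and 1 SD). State the formula and whether weights attach to values or to whole datasets.
3. For each departure, report the attainable range of the reweighted mode difference, the shift actually achieved and the effective number of imputations.
4. Cite the check as support only where the departure lies inside that range with an adequate effective number, the threshold being fixed beforehand. Elsewhere rely on the pattern-mixture shift in method (2), with its size and delivery mode stated.

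The cost is SAP wording and computing time; no new data are needed. The downside is that the non-inferiority claim may look less robust than the check as now written would suggest.
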